9.3.2. Endpoints

The BSRBR-RA is an existing, efficient data collection system for evaluating a range of safety outcomes associated with therapies used to treat RA including cancers,^{11,18} cardiovascular events¹⁹ and serious infections.¹⁷ The endpoints collected in BSRBR-RA are events associated with RA itself and therapies used to treat moderate to severe disease. The following events of interest have been pre specified for this study.

1. Hospitalised infections overall.
2. NMSC.
3. Cardiac disorders: including but not limited to heart failure, coronary artery disease, myocardial infarction, and other cardiac disorders.
4. Malignancies, excluding NMSC.
5. Events associated with use during pregnancy.

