9.7. Data Analysis

All statistical analyses will be performed by BSRBR using Stata. The annual analyses will include all patients who have received Ruxience (baseline characteristics) and event incidence reports will include all patients with study follow-up data.

Analyses will be undertaken at 12 monthly intervals and will include recruitment details, baseline characteristics and crude event rates.

The final analysis will provide the incidence rates of safety events of interest overall. If sample size allows, additional analysis in subgroups by gender and new users versus switcher from originator will be undertaken.

The general analytic approach will be descriptive and include rates of events of interest among Ruxience-treated patients. Data will be presented as number of events, incidence rates and 95 % confidence intervals. Such analyses will be performed by and at the direction of BSRBR based on an a priori statistical analysis plan (SAP) maintained by University of Manchester and shared with the Sponsor. The codes will be harmonised with other registers conducting similar analysis. A draft set of MedDRA codes is included in:

Index Date

The Index Date is the date of Ruxience initiation. Patients who switch from another therapy to Ruxience while they are enrolled in BSRBR-RA are eligible for enrollment, and the index date will be the date of Ruxience initiation.

Risk Window

Patients will be evaluated for safety events of interest while exposed to Ruxience and accrue person-time from Index Date until the first occurrence of the event of interest, death, date of last scheduled clinical data provision to the register, lost to follow up, exit from the register or completion of 3 years of follow up. The final report will censor all patients at 3 years after Date of Study Start. Follow up will be uniquely determined for each safety endpoint of interest.

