Some outcomes of interest in this study are thought to potentially occur at a higher rate while on the drug, but that increased risk subsides after the drug is discontinued (ie, serious infections, CV events). In these situations, these events will be calculated using a risk window from Ruxience initiation until 270 days (eg, 9 months) after last infusion based on Ruxience's half-life and mechanism of action. This does not apply to patients who were lost to follow-up, have exited the registry, completed 3 years of follow-up or for whom the most recent date of clinical data provision to the register is within the 270 day window, in which case data will be censored on that date instead. Based on The National Institute for Care and Health Excellence (NICE) guidelines on the use of rituximab treatment, most patients will not be considered for further treatment with Ruxience until at least 6 months from the date of last infusion.

For non-melanoma skin cancer (NMSC) and other malignancies, the manifestation of which is expected to be delayed relative to the time of exposure, the outcomes will be evaluated from drug initiation until the first event, loss to follow up or completion of 3 years of follow up, reflecting a once exposed always at risk paradigm.

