9.8. Quality Control

BSRBR-RA have guidelines in place to monitor and maintain the quality of the data received. All information received on serious adverse events are reviewed by 1 of 2 trained registered nurses prior to coding. Reports can be sent from hospitals treating the patient, the patients themselves, or the national registers. Reporting malignancies to the national cancer registries is mandatory by law in the UK. To allow serious adverse events to be processed, the following information is required as a minimum:

- A legible and recognised disorder/sign/symptom;
- The date of event;
- Which targeted therapy drug(s) the patient was on at the time of the event.

Where information is missing, the BSRBR-RA pharmacovigilance team contacts the hospital to validate and confirm the details around the serious adverse event. Where a serious adverse event is patient reported, a request for information is sent to the hospital for validation. Events that do not fall under the definition of a serious adverse event are not subject to such validation. The data undergo regular validation checks both manually and automatically.

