9.9. Limitations of the Research Methods

This study is designed to assess the safety of Ruxience within the clinical practice setting utilising the BSRBR-RA, a well-established UK based rheumatology register.

The RA treatment landscape has evolved over time with the introduction of new therapies, treatment recommendations, and approaches to managing these events. The rates of events of interest and their distribution among patient types may have changed over time.

Endpoint misclassification is of particular concern within the observational setting due to less stringent monitoring relative to clinical trials. While the BSRBR-RA has an established system to identify and capture endpoint data, it is not feasible in such an observational study to verify all events via source documentation. It is also possible that some events will be missed as all reporting is done via the rheumatology departments. If rheumatologists are not aware of an event, they cannot report it and could result in underestimation of the incidence rate. For the serious events included in this analysis this is of low probability.

This study will continue for a period of 3 years after study start (assuming it is feasible to continue participation and that a sufficient number of Ruxience-treated patients can be enrolled). This period of time may not be sufficient to assess some events, particularly malignancies which may have a longer latency period. Another limitation is the absence of a control group which does not allow for the comparison of incidence rates among Ruxience exposed patients to patients exposed to other treatments. Conclusions may not be generalisable outside of the 3 year period since initiation of therapy.

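### The cardiac endpoint is open-ended, has no seriousness criterion, contradicts the Table 2 code list, and pools all event types under one first-event clock

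*Protocol*

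**What the plan says.** Protocol section 9.3.2 introduces its endpoints as pre-specified. The third is "Cardiac disorders: including but not limited to heart failure, coronary artery disease, myocardial infarction, and other cardiac disorders". The first, by contrast, is limited by severity, "Hospitalised infections overall", and malignancy is divided into NMSC and all other cancers.

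Section 9.7 has patients "accrue person-time from Index Date until the first occurrence of the event of interest" and adds: "Follow up will be uniquely determined for each safety endpoint of interest". For cardiovascular events, "these events will be calculated using a risk window from Ruxience initiation until 270 days" after the last infusion, and "The final report will censor all patients at 3 years after Date of Study Start". The final analysis gives overall rates for the events of interest. Subgroups, if numbers allow, are by gender and by new user versus switcher. No cardiac component is named for separate reporting.

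On seriousness, section 9.4 describes the event source as serious morbidity reported by the rheumatology team and coded in MedDRA. Section 9.8 states: "Events that do not fall under the definition of a serious adverse event are not subject to such validation". Section 9.9 accepts that events unknown to the rheumatologist may be missed, then reassures: "For the serious events included in this analysis this is of low probability".

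Table 2 in Annex 1, which 9.7 calls a draft, gives the BSRBR codes for cardiovascular risk. Infarction and stroke terms count whether fatal or not. Cardiac failure and many vascular terms count only when fatal. The column heading says the list will be settled according to the endpoints reported.

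**The concern.** The protocol holds two definitions of one endpoint, and they disagree on common and clinically important events. Non-fatal heart failure counts under 9.3.2 and not under Table 2; stroke is the reverse. Because person-time ends at the first qualifying event, the choice changes both numerator and denominator. Leaving the list to be settled by what is reported allows the definition to be chosen after the counts are known.

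Even with one agreed list, a pooled first-event rate answers little. The risk management plan's concern is impact on cardiovascular disease. The same pooled rate can arise from quite different infarction and heart failure rates, and a first event of one type removes the patient from risk for the others.

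**Working it through.** **1. The two definitions side by side**

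| Event | Section 9.3.2 | Table 2, BSRBR column |
|---|---|---|
| Myocardial infarction | counts | counts, fatal or not |
| Heart failure, non-fatal | counts | does not count |
| Heart failure, fatal | counts | counts |
| Coronary artery disease other than infarction | counts | no term of that name |
| Rhythm disorders | fall under other cardiac disorders | no term listed |
| Stroke | not named; not a cardiac disorder | counts, fatal or not |
| Seriousness criterion | none | fatality, for part of the list |
| Closed list | no | enumerated, but not final |

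The stated objective is cardiovascular events and Table 1 has a row for CV events. Neither settles which column applies.

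**2. The plan's own figure**

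Table 1 gives 3 of 73 for CV events. The exact (Clopper-Pearson) interval has lower limit beta quantile (0.025; 3, 71) = 0.009 and upper limit beta quantile (0.975; 4, 70) = 0.115, with 3/73 = 0.041. The table is reproduced, and no figure in it is disputed.

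**3. What the single clock costs**

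The documents give no component rates, so these are assumptions: infarction rate m = 0.004 per person-year; other cardiac events o = 0.02 or 0.04 per person-year; infarction hazard multiplied by h = 1, 3 or 5 after a first other cardiac event; entry uniform over the 3 years, so follow-up T is uniform on 0 to 3 years. The 270-day window and death are ignored.

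Infarction as a share of the composite's first events is m/(m+o): 0.004/0.024 = 17% and 0.004/0.044 = 9%.

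Probability that an infarction is the first composite event, and so is counted: F(T) = m/(m+o) × [1 − exp(−(m+o)T)].

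Probability that an infarction follows another cardiac event, and so is not counted: A(T) = ∫ from 0 to T of o·exp(−(m+o)t) × [1 − exp(−h·m·(T−t))] dt.

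Both are averaged over T. The share lost is A/(A+F).

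| o per 1000 person-years | h | F per 1000 patients | A per 1000 patients | Share lost |
|---|---|---|---|---|
| 20 | 1 | 5.86 | 0.12 | 2.0% |
| 20 | 3 | 5.86 | 0.35 | 5.6% |
| 20 | 5 | 5.86 | 0.58 | 9.0% |
| 40 | 1 | 5.74 | 0.23 | 3.9% |
| 40 | 3 | 5.74 | 0.69 | 10.7% |
| 40 | 5 | 5.74 | 1.14 | 16.6% |

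Even in the worst row the loss is about one infarction per 1000 patients. The composition of the endpoint matters more: under these rates 83 to 91% of first events are not infarctions.

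**The case against.** A reader might infer from 9.3.2 that a minor or unvalidated event, such as a rhythm disturbance, would stop the clock. The documents do not support this. Section 9.4 describes serious morbidity, 9.8 has serious adverse event information reviewed by trained nurses, and 9.9 calls the analysed events serious. The validation exemption in 9.8 suggests that some non-serious reports arrive, but nothing says they enter this analysis. Table 2 has no rhythm term. What remains is that 9.3.2 never states the restriction on which the reassurance in 9.9 depends.

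A reader might also infer that infarction and heart failure rates will never be estimated. The protocol neither promises nor excludes them, and it defers to a SAP that is not shown and may add such rows. Nor does a cardiac event end follow-up altogether: only the cardiac clock stops.

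It can further be said that a first-event composite is conventional in a descriptive study without hypotheses, that the other endpoints are broad too, and that the loss is small beside the Table 1 interval. The 270-day window also shortens cardiac follow-up in patients who stop treatment, so the shares above tend to overstate the loss for them. All of this stands, and it is why the clock is the lesser part of the point. It does not touch the contradiction between 9.3.2 and Table 2. Both are in the protocol, and an unfinished list cannot resolve it.

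**Conclusion.** The point holds in this form: the protocol defines its cardiac endpoint in two incompatible ways, gives no seriousness criterion in the endpoint itself, and leaves the code list to be settled after events are reported. That conclusion rests on the text alone.

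The single first-event clock is a secondary defect of modest size: about 2 to 4% of infarctions lost with unchanged risk, 6 to 11% with a threefold rise and 9 to 17% with a fivefold rise, all under assumed rates and without the 270-day window. The main gain from correcting it is a cardiac result that can be interpreted. The endpoint should be corrected; the planned analysis does not otherwise fail because of it.

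**What to change.** 1. Reconcile 9.3.2 and Table 2 into one closed list of serious events: fatal, hospitalised or otherwise meeting the register's SAE definition. State explicitly whether stroke belongs. Editing 9.3.2 and 9.7 alone would leave Table 2 in conflict.
2. Fix the list before event data are reviewed. Section 9.7 includes crude event rates in the 12-monthly analyses, so this means before the first of them. Remove the provision that it depends on the endpoints reported.
3. Keep the composite rate. Beside it, report first-event rates for myocardial infarction, heart failure and other serious cardiac events, each with its own clock within the 9.7 cardiovascular risk window, so that one component does not end follow-up for another. If stroke is kept, give it its own row.

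The cost is wording in 9.3.2, 9.7 and Table 2, and a few extra rows from MedDRA codes the register already assigns. The downside is lower precision per component. In Table 1, 3 of 73 has an upper limit 2.8 times its estimate (0.115/0.041); 1 of 73, as in the malignancy row, has one 5.3 times its estimate (0.074/0.014).

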9.4. Data Sources

BSRBR is the source of core baseline data, including patient demographics and disease characteristics collected by the recruiting clinician, using a standardised form.

Follow up

BSRBR data are the source of information on anti-rheumatic treatment, updated every 6-12 months depending on how long a patient has been in the register (6 monthly for the first 3 years and 12 monthly thereafter). This change is to reduce the burden of data capture on study sites, but the same data are collected at each follow-up. As many patients starting Ruxience will have been enrolled previously when they started Mabthera, follow-up may only be every 12 months. Some patients starting Ruxience as their first anti-B cell therapy will provide data more often as per the BSRBR protocol and some trusts may decide themselves to reconsent patients each time they switch drugs and send data every 6 months for 3 years again. Data captured includes continuation on drug and dates and reasons for stopping, with details of any change in dose and commencement of any new co therapy. Clinical information to permit calculation of the Disease Activity Score in 28 joints (DAS-28) is also collected.

Endpoints

BSRBR data include reports of serious morbidity reported directly by the rheumatology team at each scheduled follow-up date. For serious events additional data are captured, either against a pre-specified set of questions for certain events of special interest or using an open request for additional data. All events included in this protocol are considered events of special interest. All serious morbidities reported to BSRBR are coded by a trained nurse using the Medical Dictionary for Regulatory Activities (MedDRA).

BSRBR is linked to the UK national death and cancer registers which allow the “flagging” of individuals such that if they die or are entered in a cancer register, the BSRBR-RA learns of the event and obtains death certificate details or cancer register details. These data are held in a separate secure data safe haven at the University of Manchester. On average deaths are usually reported within 1 week to the national register although cancers can take much longer due to the structure of national reporting. BSRBR-RA received a download of death and cancer on average once/year.

9.5. Study Size

This is a descriptive study without pre-specified hypotheses, therefore there is no minimum sample size requirement. All Ruxience-treated patients with data in the BSRBR-RA during the study period will be included in this study. Table 1 displays precision estimates for reported incidence proportions of safety events in Ruxience RMP.

Table 1. Precision Estimates for Reported Incidence Proportions of Safety Events in Ruxience RMP²

Condition	Incident Count	Population at Risk	Incidence Proportion	Lower Bound of 95% CI	Upper Bound of 95% CI
Any infection (including serious infection)	22	73	0.301	0.199	0.420
Serious infection	3	73	0.041	0.009	0.115
Malignancy (excluding NMSC)	1	73	0.014	0.000	0.074
NMSC	0	73	0.000	0.000	0.049
CV events	3	73	0.041	0.009	0.115
Events during pregnancy	0	73	0.000	0.000	0.049

NMSC, non-melanoma skin cancer; CV, cardiovascular; CI, confidence interval.

9.6. Data Management

All data are submitted by the local hospital sites to the University of Manchester via a secure online web portal. The BSRBR-RA data capture system is a web-based (<https://bsrbr.org/database/>), access managed, secure system hosted on the University of Manchester virtual secure servers which is accessed by 160 NHS clinical sites across the UK. NHS clinical staff use the web interface to log into their restricted area, enter and submit clinical data and efficiently communicate with study staff. The system uses encryption in transit and at rest and secure web authentication. Further details are provided here.

The investigator must obtain Pfizer's written permission before disposing of any records, even if retention requirements have been met.

9.7. Data Analysis

All statistical analyses will be performed by BSRBR using Stata. The annual analyses will include all patients who have received Ruxience (baseline characteristics) and event incidence reports will include all patients with study follow-up data.

Analyses will be undertaken at 12 monthly intervals and will include recruitment details, baseline characteristics and crude event rates.

The final analysis will provide the incidence rates of safety events of interest overall. If sample size allows, additional analysis in subgroups by gender and new users versus switcher from originator will be undertaken.

The general analytic approach will be descriptive and include rates of events of interest among Ruxience-treated patients. Data will be presented as number of events, incidence rates and 95 % confidence intervals. Such analyses will be performed by and at the direction of BSRBR based on an a priori statistical analysis plan (SAP) maintained by University of Manchester and shared with the Sponsor. The codes will be harmonised with other registers conducting similar analysis. A draft set of MedDRA codes is included in:

Index Date

The Index Date is the date of Ruxience initiation. Patients who switch from another therapy to Ruxience while they are enrolled in BSRBR-RA are eligible for enrollment, and the index date will be the date of Ruxience initiation.

Risk Window

Patients will be evaluated for safety events of interest while exposed to Ruxience and accrue person-time from Index Date until the first occurrence of the event of interest, death, date of last scheduled clinical data provision to the register, lost to follow up, exit from the register or completion of 3 years of follow up. The final report will censor all patients at 3 years after Date of Study Start. Follow up will be uniquely determined for each safety endpoint of interest.

Some outcomes of interest in this study are thought to potentially occur at a higher rate while on the drug, but that increased risk subsides after the drug is discontinued (ie, serious infections, CV events). In these situations, these events will be calculated using a risk window from Ruxience initiation until 270 days (eg, 9 months) after last infusion based on Ruxience's half-life and mechanism of action. This does not apply to patients who were lost to follow-up, have exited the registry, completed 3 years of follow-up or for whom the most recent date of clinical data provision to the register is within the 270 day window, in which case data will be censored on that date instead. Based on The National Institute for Care and Health Excellence (NICE) guidelines on the use of rituximab treatment, most patients will not be considered for further treatment with Ruxience until at least 6 months from the date of last infusion.

For non-melanoma skin cancer (NMSC) and other malignancies, the manifestation of which is expected to be delayed relative to the time of exposure, the outcomes will be evaluated from drug initiation until the first event, loss to follow up or completion of 3 years of follow up, reflecting a once exposed always at risk paradigm.

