9.2.1. Inclusion Criteria

1. Eligible for inclusion in BSRBR-RA;
2. Newly initiated treatment with Ruxience for RA;
3. Age >16 years at the initiation of Ruxience treatment.

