10.2. Patient Consent

As this study involves anonymised structured data, which according to applicable legal requirements do not contain data subject to privacy laws, obtaining informed consent from patients by Pfizer is not required. The University of Manchester will obtain written informed consent from all patients prior to data collection.

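### Person-time starts at Ruxience initiation although entry does not require registration by then, so any gap before registration is counted as at-risk time

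*Protocol*

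**What the plan says.** Protocol 9.7 defines time zero once for all patients: "The Index Date is the date of Ruxience initiation". Under Risk Window, patients "accrue person-time from Index Date until the first occurrence of the event of interest" or one of the listed censoring dates. For serious infections and CV events the window is a "risk window from Ruxience initiation until 270 days (eg, 9 months) after last infusion". For NMSC and other malignancies it also starts at drug initiation. Neither rule mentions the date of registration.

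Entry is set in 9.2.1. Criterion 1 is "Eligible for inclusion in BSRBR-RA" and criterion 2 is "Newly initiated treatment with Ruxience for RA". Neither asks that registration precede the first infusion, and no maximum gap is given. Section 9.5 adds: "All Ruxience-treated patients with data in the BSRBR-RA during the study period will be included in this study".

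On consent, 10.2 says: "The University of Manchester will obtain written informed consent from all patients prior to data collection". In the operational sections, enrolment is placed before initiation only for switchers: "Patients who switch from another therapy to Ruxience while they are enrolled in BSRBR-RA are eligible for enrollment". The limitations in 9.9 do not mention delayed entry.

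**The concern.** Incidence rates are this study's only inferential output, so the denominator matters. If a patient starts Ruxience and joins the register weeks or months later, someone comparable who died in between is never in the cohort. The survivor's gap nevertheless counts as time at risk. This is left truncation handled as if it were follow-up, and it lowers the rate of any event that cannot be observed in the gap.

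Fatal events are part of an actual endpoint: the CV definition for BSRBR in Annex 1, Table 2 has a list of terms that count with fatal or non-fatal outcome and a long list that counts only when fatal. The period lost is also the one straight after first exposure. Patients already registered when they start Ruxience have no gap, so any bias would fall unevenly across the cohort.

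**Working it through.** **Is there a figure in the plan to reproduce?** None for the lag, person-time or expected rates. The only planning figures are the precision estimates in Table 1 (9.5). Exact Clopper-Pearson limits with n = 73 reproduce all six rows, for example serious infection 3/73 = 0.041 (0.009 to 0.115). They do not bear on when person-time starts.

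**Inputs.** From the protocol: start of person-time at initiation, calendar censoring of all patients 3 years after study start, and a 270-day window after the last infusion (9.7). Assumed, because the protocol gives neither: the lag L from initiation to registration, and the share p of initiators who register late. Further assumptions: uniform uptake over 3 years, constant hazard, and no gap events captured. The last holds for death and fatal events and is an upper bound for others.

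**Long window (follow-up to the 3-year censoring date).** A late registrant enters only if potential follow-up exceeds L, which has probability 1 − L/3.

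- Immortal time per late initiator: (1 − L/3) × L
- Counted time per late initiator: (1 − L/3) × (3 + L)/2
- Counted time per already-registered patient: 1.5 years
- Overall understatement: p(1 − L/3)L ÷ [p(1 − L/3)(3 + L)/2 + (1 − p) × 1.5]

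| Lag | Immortal (years) | Counted (years) | Share in late registrants | Overall, p = 0.3 | Overall, p = 0.5 |
|---|---|---|---|---|---|
| 1 month | 0.081 | 1.499 | 5.4% | 1.6% | 2.7% |
| 3 months | 0.229 | 1.490 | 15.4% | 4.6% | 7.7% |
| 6 months | 0.417 | 1.458 | 28.6% | 8.4% | 14.1% |

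One cell in full (3 months, p = 0.5): 0.5 × 0.229 ÷ (0.5 × 1.490 + 0.5 × 1.5) = 0.1146 ÷ 1.495 = 7.7%.

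**Shortest window (infections and CV events).** With a window of W days, observed/true = 1 − p × L/W. The extreme case is a patient with one infusion date and no retreatment, W = 270. A 90-day lag then gives 1 − 90/270 = 0.67 in late registrants, and 1 − 0.5 × 90/270 = 0.83 overall if half register late. Retreatment lengthens W and shrinks the effect: at W = 1096 the first figure becomes 1 − 90/1096 = 0.92.

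**Does delayed entry repair it?** A simulation of 2,000,000 patients at an illustrative 41 events per 1000 person-years compared the rate counted from registration with the true full-window rate. Windows were 270, 548 and 1096 days, and lags were 30, 90 and 180 days.

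- Constant hazard: ratio 0.998 to 1.002, so the bias is removed.
- Hazard doubled in the first 90 days: ratio 0.74 to 0.97. Delayed entry does not recover early risk that nobody observed.

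With L = 0 the bias is nil. It is also nil if all gap events are captured and nobody dies before registration.

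**The case against.** The strongest reply is that the triggering fact is absent. Nowhere does the protocol say that patients register after their first infusion. The abstract describes the population as patients enrolled in the register who initiate Ruxience, and its study start definition can be read the same way. That stands as far as occurrence and size are concerned. It does not settle the rule: section 8 words the research question in the reverse order, and the entry criteria themselves ask only for eligibility.

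A reader might infer that every rate is biased downward. The documents do not support this. Section 10.2 limits when data are collected, not which event dates may be recorded. Under 9.8, reports can come from hospitals, patients or national registers and carry an event date. Under 9.4, cancers also arrive by linkage. Non-fatal gap events may therefore be captured. Death and fatal events in the gap cannot be.

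A reader might also infer that new users would look safer than switchers as an artefact. That equates new rituximab users with newly registered patients. Rituximab is indicated after other DMARDs including at least one TNF inhibitor (section 7), the register recruits TNFi-treated patients (9.2), and 9.7 admits switches from any therapy. Some new users will already be registered and have no gap. The overlap is partial at most, and the subgroup analysis is conditional on sample size.

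Section 9.5 should not be over-read either: it concerns study size, and criterion 2 still requires new initiation.

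Leaving the matter to the SAP is not a full answer. The protocol is not silent on time zero. It fixes a start of person-time, and an SAP that followed it would carry the problem forward.

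**Conclusion.** The point holds in conditional form. The protocol states a time-zero rule that counts immortal time for anyone registered after the first infusion, and nothing in it excludes such patients. For them the downward bias is certain for death and fatal events, and possible for other events, depending on whether gap events are recorded.

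The size is unknown. With a 1 to 6 month lag in 30 to 50% of patients, overall rates over follow-up to the 3-year censoring date would be understated by at most about 2 to 14%, and by nothing without a lag. That ceiling assumes constant hazard. A higher early hazard, or the single-course 270-day window, would raise it. Dilution is likely, since 9.4 expects many patients to have been enrolled already on MabThera. The bias could differ between newly registered and already-registered patients, but the documents do not show that it would reverse or create a difference in the planned subgroups.

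**What to change.** Keep the Index Date at Ruxience initiation and leave the ends of the risk windows as they are. Then:

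- In 9.7, accrue person-time and count events in the primary rate from the later of the Index Date and the date of BSRBR-RA registration (consent).
- In 9.2.1, change criterion 1 to require registration in BSRBR-RA. Align 9.5, so that a patient whose Ruxience start precedes registration contributes only from registration.
- List any recorded events between initiation and registration separately, so that they are not lost from the safety record.
- Report the distribution of the initiation-to-registration lag, split by new user and switcher, so that readers can judge how much early risk went unobserved.

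The cost is a few sentences, assuming that the register holds both dates. The downside is a small loss of early person-time and of early events from the primary rate. If no patient registers late, the results do not change.
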